## 1. Introduction

This document outlines the efficacy statistical analysis plan (SAP) for the protocol STAND, a phase 3 trial of three experimental regimens of the combination regimen of moxifloxacin, PA-824 and pyrazinamide (MPaZ).

The primary efficacy analysis will be conducted using culture results from liquid culture (MGIT) and will evaluate the hypothesis that in the patients with drug-sensitive tuberculosis (DS-TB) treated with any of the experimental MPaZ regimens, the incidence of bacteriologic failure or relapse or clinical failure at 12 months from the start of therapy is non-inferior to the proportion observed in patients who are treated with the 6 month standard isoniazid, rifampicin, pyrazinamide, ethambutol (HRZE/HR) regimen.

The three experimental regimens detailed below will be compared to the control regimen in the order specified. For the second and third comparison, statistical inference will only be made if non-inferiority is declared on the preceding comparison:

*First comparison:* MPaZ with 200mg PA-824 (MPa200Z) for 6 months vs HRZE/HR

*Second comparison:* MPaZ with 200mg PA-824 (MPa200Z) for 4 months vs HRZE/HR

*Third comparison:* MPaZ with 100mg PA-824 (MPa100Z) for 4 months vs HRZE/HR

300 patients per randomised arm will be recruited. See Appendix 1 for details of the sample size. An additional non-randomised group of up to 300 patients with multi-drug resistant (MDR) TB will be treated with regimen MPa200Z for 6 months. No formal statistical analysis is planned for this group and unless otherwise stated all analyses outlined in this document refer to the analysis of the 4 randomised groups of the DS-TB patients.

While STAND is an open label study, only members of the Data Safety Monitoring Committee (DSMC) and the unblinded statistician(s) will have access to data **grouped by study arm**. Access to data by investigators, CRO and TB Alliance staff will not allow any access to data grouped by study arm. In addition, site staff will be strongly discouraged from attempting to aggregate by treatment arm at a site level.

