## 4. Analysis populations

The analysis populations for efficacy analyses are:

- The **All Randomised** population defined as all patients randomised with no exclusions
- The **Intent to treat (ITT)** population is defined as All Randomised excluding late screening failures (see 4.1)
- The **Modified intent to treat (MITT)** population is defined as the ITT population with extra exclusions (See 4.2)
- The **Per-protocol (PP)** population is defined as the MITT population with extra exclusions (see 4.3)

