#### **4.1. Exclusions from ITT analysis (late screening failures)**

1. Patients randomised into one of the DS arm who on subsequent receipt of the results of the MGIT drug sensitivity tests are found to be rifampicin and/or pyrazinamide and/or fluoroquinolone resistant and/or INH mono-resistant) documented from Day 1 (baseline) sputum samples (or screening or out to Week 4 if the baseline is contaminated or negative) (late exclusions from the study). These patients will be withdrawn from the study.
2. Patients without culture confirmation of M. tb at Day 1 (baseline) sputum samples (or screening or out to Week 4 if the baseline is contaminated or negative) (late exclusions from the study)
3. Patients withdrawn from treatment because of a protocol violation at enrolment (late exclusions from the study, based on data collected prior to randomisation).

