### **6.1.3. Unfavourable status in MITT population**

1. Patients not classified as having achieved or maintained culture negative status when last seen, or
2. Patients previously classified as having culture negative status who, following the end of treatment, have two positive cultures without an intervening negative culture, (however, see Section 3.3 for an exception), or
3. Patients who had a positive culture not followed by at least two negative cultures when last seen, or
4. Patients dying from any cause during treatment, except from violent or accidental cause (e.g. road traffic accident), not including suicide (eg, suicide will be considered an unfavourable outcome) or
5. Patients definitely or possibly dying from TB related cause during the follow-up phase or
6. Patients requiring an extension of their treatment beyond that permitted by the protocol, a restart or a change of treatment for any reason except reinfection or pregnancy, or
7. Patients failing to complete an adequate course of treatment, as defined in section 4.5, who were unassessable at 12 months, or
8. Patients lost to follow up or withdrawn from the study before the end of treatment

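### Section 4.1(3) removes enrolment violators from ITT and MITT only if they were withdrawn from treatment, an open-label decision after randomisation, so events can be lost unequally between arms

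*SAP*

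**What the plan says.** SAP section 4 defines ITT by exclusion: the "population is defined as All Randomised excluding late screening failures (see 4.1"). MITT in turn is the "population is defined as the ITT population with extra exclusions (See 4.2"), and PP the "population is defined as the MITT population with extra exclusions (see 4.3"). Whoever is removed under 4.1 is absent from all three main analyses.

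Section 4.1 lists three kinds of late screening failure. Items 1 and 2 rest on laboratory results: drug resistance, and absence of culture confirmation. Item 3 covers "Patients withdrawn from treatment because of a protocol violation at enrolment", with a parenthesis that labels them late exclusions and ties the violation to pre-randomisation data.

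Other withdrawals are treated differently. Section 4.4 counts early withdrawals before the end of treatment as unfavourable in ITT and MITT. Section 6.1.2 makes every ITT patient without a favourable outcome unfavourable. Section 6.1.3(8) lists as unfavourable in MITT "Patients lost to follow up or withdrawn from the study before the end of treatment". Section 4.3 removes from PP patients withdrawn before the end of treatment (item 1), those without adequate treatment (item 3) and major protocol deviators (item 4), in each case with a proviso for patients already unfavourable.

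On blinding, section 1 begins "While STAND is an open label study" and then restricts access to data grouped by arm. It does not conceal a patient's own regimen from the site.

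**The concern.** An exclusion after randomisation is harmless to the comparison when it depends only on facts fixed before randomisation and is applied alike to every patient. Item 3 meets the first condition for the evidence but not for the trigger. The parenthesis limits which data may establish the violation; it does not say that every patient with such a violation is excluded. Whether a violator leaves ITT and MITT depends on whether treatment was stopped, and that can depend on the regimen and on how the patient is doing.

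The patients concerned are also likely events. Without item 3, a patient taken off treatment would normally count as unfavourable in ITT and MITT, so item 3 turns a would-be event into an exclusion. If sites stop violators more readily in one arm, that arm's unfavourable rate falls for reasons unrelated to efficacy. MITT is one of the two analyses that sections 2 and 7 call primary, and the conclusion rests on a confidence bound against 12%.

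**Working it through.** **1. Two patients with the same violation**

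| | Kept on treatment | Withdrawn because of the violation |
|---|---|---|
| ITT | Included, classified on outcome | Excluded, 4.1(3) |
| MITT | Included, unless a 4.2 exclusion applies | Excluded, by nesting |
| PP | Included, or out under 4.3(4) if a major deviation | Excluded by nesting; without 4.1(3) would normally leave anyway under 4.3(1) or 4.3(3) |

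The two patients differ only in a decision taken after randomisation. In ITT and MITT that decision determines inclusion. In PP it adds little: item 3 matters there mainly for a patient already classified unfavourable, whom the 4.3 provisos would otherwise keep in.

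**2. Safeguards elsewhere in the SAP.** Categories 1 to 5 of section 4.2 do not apply to patients already unfavourable; 4.2(6) and all four items of 4.3 carry similar provisos. Section 4.1(3) has none. Section 4.6 requires cause of death to be reviewed blind to arm. Section 4.1 requires no such review for item 3, and gives neither a list of qualifying violations nor a time limit.

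**3. Size of the shift.** The SAP states no figure for enrolment violators, so there is none to reproduce, and the counts below are assumed. From Appendix 1: 300 recruited per arm, 8% excluded for isoniazid mono-resistance, 16% unfavourable. Then N = 300 × 0.92 = 276. Let the true rate be 16% in both arms, and let *k* violators with unfavourable rate *q* be excluded from one arm only.

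Rate after exclusion = (0.16 × 276 − *qk*) / (276 − *k*); shift = that rate − 0.16.

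Example, *k* = 3, *q* = 1: (44.16 − 3)/273 = 15.08%, a shift of −0.92 points.

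| *k* | *q* = 0.16 | *q* = 0.5 | *q* = 1 |
|---|---|---|---|
| 3 | 0.0 | −0.4 | −0.9 |
| 6 | 0.0 | −0.8 | −1.9 |
| 9 | 0.0 | −1.2 | −2.8 |

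The shift is in the rate of the arm that loses the patients. Lost from an experimental arm, they lower the risk difference; lost from control, they raise it by the same amount.

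**4. Against the margin.** Take 231 per arm (300 × (1 − 0.15 − 0.08), using Appendix 1's 15% unassessable) and the unadjusted Wald bound: difference + 1.96 × √[p₁(1−p₁)/n₁ + p₀(1−p₀)/n₀].

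- 48/231 against 37/231: 4.76 + 7.05 = 11.8%, passes. Return two excluded experimental-arm patients as unfavourable, 50/233 against 37/231: 5.44 + 7.08 = 12.5%, fails.
- The reverse, 49/231 against 37/231: 5.19 + 7.08 = 12.3%, fails. Return two excluded control patients as unfavourable, 49/231 against 39/233: 4.47 + 7.13 = 11.6%, passes.
- Two returned to each arm in the first case, 50/233 against 39/233: 4.72 + 7.12 = 11.8%, still passes.
- Away from the margin, 37/231 in both arms: bound 6.7%. Two experimental events returned, 39/233 against 37/231: about 7.5%, still passes.

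A conclusion changes only when the result is already at the margin and the exclusions are unbalanced.

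**The case against.** The strongest reply is that item 3 sits under late screening failures and is tied to data from before randomisation. Item 1 of the same list says that its patients will be withdrawn from the study; item 3 can be read in the same spirit, with withdrawal following automatically once ineligibility is found. If the protocol makes withdrawal mandatory, there would be few retained violators and the contrast largely disappears. That is fair, and the protocol is not at hand. The SAP wording still makes withdrawal the condition, so it relies on a uniformity that it does not itself secure.

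Second, section 8 plans an analysis of all randomised patients, and section 7 asks for sensitivity analyses to be consistent before non-inferiority is declared. This has weight, but it is partial. That analysis also restores the resistant and culture-unconfirmed patients (at 8%, isoniazid mono-resistance alone is 300 × 0.08 = 24 per arm), so it cannot isolate item 3, and section 7 does not require every supporting analysis to meet the margin.

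Third, 6.1.3(8) speaks of withdrawal from the study and item 3 of withdrawal from treatment. The terms do differ. However, 4.4 covers early withdrawal generally, and 6.1.3(6) and (7) make a change of treatment, or inadequate treatment with an unassessable outcome, unfavourable as well.

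A reader might infer two stronger things. One is that the rule favours the experimental arms: nothing in the SAP shows or implies that violators would be withdrawn more often there, and the rule is worded alike for all arms. The other is that it distorts all three main analyses equally: nesting carries the exclusion into PP, but most of these patients would leave PP anyway.

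**Conclusion.** The point stands as a minor, inexpensive improvement. Removal from ITT and MITT under 4.1(3) depends on a decision made after randomisation with the arm known, without arm-blind review and without a proviso for patients already unfavourable. It can take events out of the arms unequally, in either direction. Unequal withdrawal is a possibility, not something the SAP shows.

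The effect is probably small. It is zero if the excluded patients have the average event rate, and about 0.9 points for three would-be unfavourable patients lost from one arm only. The examples that cross the 12% margin were chosen to lie at it: with 37/231 in control, 48 is the last passing count among 231. They use assumed, unbalanced counts and an unadjusted interval, whereas the SAP's primary analysis is stratified by HIV status and cavitation. No sample-size figure is affected.

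**What to change.** Replace item 3 of section 4.1 with an exclusion defined by the violation itself, for example: *patients found, on review of pre-randomisation data blind to arm, to have violated a listed eligibility criterion, whether or not withdrawn from treatment*. Apply it to all randomised arms, name the qualifying criteria, and fix the list of patients before database lock, with arm-blind review as section 4.6 already provides for deaths. Because exclusion would then depend only on pre-randomisation facts, no proviso for patients already unfavourable would be needed.

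The change concerns the analysis population only; it does not touch who is taken off treatment. It costs one sentence in the SAP and a blind check of eligibility data already held. The downside is that a few violators who completed treatment and have outcomes would also be excluded, which moves ITT slightly further from all randomised patients. If that is unwelcome, keeping all such patients in ITT also removes the dependence on withdrawal there; MITT would then need the same choice stated.

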#### **4.2. Additional exclusions from MITT analysis**

1. Patients who, having completed treatment, are lost to follow-up or withdrawn from the study, their last status being culture negative and their last positive culture result (“isolated positive culture”) followed by at least two negative culture results at different visits (at least 7 days apart, without an intervening positive culture)
2. Women who become pregnant during treatment and stop their allocated treatment
3. Patients who died during treatment from violent or accidental cause (e.g. road traffic accident). N.B.: This does not include death from suicide, which will be considered an unfavourable outcome.
4. Patients who died during follow-up (after the end of treatment) with no evidence of failure or relapse of their TB, their last status being culture negative and their last positive culture result (“isolated positive culture”) followed by at least two negative culture results at different visits (at least 7 days apart), and who have not already been classified as unfavourable.
5. Patients who, after being classified as having culture negative status, are re-infected with a new strain from that with which they were originally infected. Reinfection will be defined specifically as a patient infected with a strain that is genetically different from the initial strain (see Mycobacteriology Laboratory Manual).
6. Patients who are able to produce sputum at 12 months, but whose 12-month visit sputum samples are all contaminated or missing, who cannot be brought back for repeat cultures, provided they have not already been classified as unfavourable and provided their last positive culture was followed by at least two negative cultures. N.B.: This does not apply to patients who are unable to produce sputum at 12 months, or to patients who are able to be brought back subsequently and produce negative cultures.

Patients in categories 1-5 above who had already been classified as having an unfavourable outcome will not be excluded.

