## 2. Primary Efficacy Endpoint

The primary efficacy endpoint will be the incidence of bacteriologic failure or relapse or clinical failure within 12 months from start of therapy. See section 6 for the detailed definition of an “unfavourable response” at 12 months.

There will be three main analyses of the primary efficacy endpoint: A per-protocol (PP) analysis, a modified intent to treat (MITT) analysis and an intent to treat (ITT) analysis. As the true bacteriologic treatment failure and relapse rate in the control group is expected to be between 3% and 5%, “unfavourable” rates in any defined ‘ITT’ population will likely be increased considerably by factors other than bacteriologic or clinical treatment failure and relapse. The PP and MITT analyses will be considered primary; results of ITT and additional sensitivity analyses (listed in section 8) will need to be consistent to draw a strong conclusion.

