**Relapse or Bacteriologic relapse** is defined as failing to maintain culture negative status or being declared an unfavourable outcome after the end of treatment (either 4 or 6 months) in those patients who attained culture negative status by the end of treatment, and were re-infected with the **same** (as per the STAND Laboratory Manual) *Mycobacterium tuberculosis (MTB)* strain.

**Reinfection or Bacteriologic Reinfection** is defined as failing to maintain culture negative status or being declared an unfavourable outcome after the end of treatment (either 4 or 6 months) in those patients who attained culture negative status by the end of treatment and were infected with a *Mycobacterium tuberculosis (MTB)* strain that is **different** (as per the STAND Laboratory Manual) from the infecting strain at baseline.

**Clinical failure** is defined as a change from protocol-specified TB treatment or retreatment for TB during follow up as determined by the treating physician, or TB-related death.

The **treatment period** is defined as either 4 or 6 months from start of therapy depending on allocated treatment regimen and the **follow-up period** is defined as the period after the end of treatment to the end of follow-up.

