## **6. Classification of primary endpoint status**

Patients will be classified as having a favourable, unfavourable or unassessable status at 12 months from the start of therapy.

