### **6.1.1. Favourable status (all analyses)**

Patients with a negative culture status at 12 months from start of therapy (from 50 weeks to 54 weeks), who had not already been classified as having an unfavourable outcome, and whose last positive culture result ("isolated positive culture") was followed by at least two negative culture results.

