### **6.1.2. Unfavourable status in ITT population**

Patients in the ITT analysis population who do not have a favourable outcome by 12 months will be considered to have an unfavourable response in the ITT analysis.

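### The MITT and PP rules on loss, non-TB death and reinfection have no 12-month limit, which conflicts with a 12-month primary endpoint in a trial followed to 24 months

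*SAP*

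**What the plan says.** **The endpoint is fixed at 12 months.** SAP 2: "The primary efficacy endpoint will be the incidence of bacteriologic failure or relapse or clinical failure within 12 months from start of therapy". SAP 6: "Patients will be classified as having a favourable, unfavourable or unassessable status at 12 months from the start of therapy". SAP 6.1.1 bases favourable status, for all analyses, on culture status at weeks 50 to 54. The ITT rule in 6.1.2 concerns "Patients in the ITT analysis population who do not have a favourable outcome by 12 months".

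**Follow-up is longer.** SAP 3.4 sets a window for a 24-month visit, and 10.1 repeats the efficacy analyses at 24 months. SAP 3.1 says that the follow-up period "is defined as the period after the end of treatment to the end of follow-up".

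**The MITT exclusions have no end date.** Three items in SAP 4.2 matter here:
- Item 1 covers loss or withdrawal after completed treatment with culture-negative status.
- Item 4 covers "Patients who died during follow-up (after the end of treatment) with no evidence of failure or relapse of their TB".
- Item 5 covers reinfection with a different strain.

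The closing sentence of 4.2 reads: "Patients in categories 1-5 above who had already been classified as having an unfavourable outcome will not be excluded". It says nothing of patients already classified as favourable. SAP 4.4 likewise treats loss after the end of treatment as unassessable in MITT and PP, with exceptions only for patients who are unfavourable, not culture negative, or have an unresolved positive. SAP 4 defines PP as MITT with further exclusions, so PP inherits all of this.

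**The unfavourable rules are also open-ended item by item.** Items 1 to 3 of 6.1.3 and 6.1.4 refer to the patient's last contact or to any time after treatment. Item 5 refers to "Patients definitely or possibly dying from TB related cause during the follow-up phase".

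**The concern.** A population rule for a 12-month endpoint should not depend on what happens after month 12. Here it can. Take two patients who both move away at month 15. The one who was favourable at week 52 meets 4.2 item 1 and is excluded. The one who was unfavourable is kept by the closing sentence. Removal on this reading acts only on favourable patients, so it raises the unfavourable rate in each arm, widens the interval, and lets second-year retention enter a 12-month non-inferiority test. If second-year loss differs between arms, which is possible in an open-label trial, the difference itself is biased.

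Status has a related conflict. A patient negative at weeks 50-54 with two positive cultures at month 18 meets 6.1.1 (favourable) and, on its wording, 6.1.3 item 2 (unfavourable). Two competent programmers could derive different primary populations and different outcomes from this text.

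**Working it through.** **1. The plan's own figure.** SAP Appendix 1 assumes 16% unfavourable, a 12% margin, 90% power, one-sided 2.5%, and 15% plus 8% not analysable.

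n = 2 × 0.16 × 0.84 × (1.960 + 1.282)² / 0.12² = 196.1 evaluable per arm; 196.1 / 0.77 = 254.7, which agrees with the stated 255. The sample size is not in dispute.

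**2. Inputs for the size of the effect.** The SAP states 300 recruited per arm, 15% unassessable, 8% excluded for isoniazid mono-resistance, and the 12% margin. Applying the two losses in turn gives 300 × 0.85 × 0.92 = 234.6, about 235 per arm. Control at about 16% is 38/235. Two things are assumed because the SAP does not give them: the experimental result, and the share of favourable patients with a later loss, non-TB death or reinfection.

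**3. Formula.** d = pE − pC; SE = √[pE(1−pE)/nE + pC(1−pC)/nC]; upper limit = d + 1.96 × SE. This is unadjusted. The SAP's primary analysis is stratified by HIV status and cavitation, so its limits would differ slightly.

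**4. A near-margin result, 48/235 against 38/235.** Favourable patients number 187 and 197. Removals are rounded to whole patients.

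| Favourable removed, experimental / control | Counts | d (points) | Upper limit (points) |
|---|---|---|---|
| none | 48/235 vs 38/235 | 4.3 | 11.2 |
| 5% / 5% | 48/226 vs 38/225 | 4.3 | 11.6 |
| 10% / 10% | 48/216 vs 38/215 | 4.5 | 12.1 |
| 15% / 15% | 48/207 vs 38/205 | 4.7 | 12.5 |
| 10% / 5% | 48/216 vs 38/225 | 5.3 | 12.7 |

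For the 10% / 10% row: 22.22 − 17.67 = 4.55; SE = 3.84; 4.55 + 1.96 × 3.84 = 12.08.

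**5. Away from the margin.** At 47 against 38 of 235, 10% removal in each arm gives 11.6, still below 12. At 38 against 38, 10% in each arm moves the limit only from 6.7 to 7.2.

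**6. Unequal removal with equal 12-month results (38/235 in each arm).** Removing 10% against 5% gives 38/215 − 38/225 = 17.67 − 16.89 = 0.8 points. Removing 15% against 5% gives 38/205 − 38/225 = 18.54 − 16.89 = 1.6 points.

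**7. Unequal removal can also favour the experimental arm.** At 50/235 against 38/235 the upper limit is 12.14. Removing 5% of favourable patients from the experimental arm and 10% from control gives 50/226 against 38/215: 22.12 − 17.67 = 4.45; SE = 3.79; upper limit 11.9.

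**8. Power.** With Appendix 1's additive losses, 300 × 0.77 = 231 evaluable per arm gives 94.0%. If 10% of all assessable patients were removed, all of them favourable, n is 208, the rate is 0.16/0.90 = 17.8%, and power is 89.3%.

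None of these figures includes relapses or TB deaths first arising after month 12, which the open wording of 6.1.3 and 6.1.4 could add as unfavourable.

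**The case against.** The strongest reply is that the 12-month horizon is stated often enough to govern everything else. Section 2 sets it. The opening sentence of section 6 stands above 6.1.3 and 6.1.4 and makes unassessable a status at 12 months, so a patient with a negative week-52 culture is not unassessable under 4.4. SAP 3.1 says that one culture result at 12 months is enough for primary classification. The undated wording has a plausible purpose: the same rules serve 12 and 24 months (10.1, and the joint mention in 3.2). If second-year events counted at month 12, the exclusions for loss, death and reinfection would be the same at both horizons. A data cut at each patient's month 12, perhaps set in the protocol, would also remove the effect.

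Much of this stands. A reader might infer that the exclusions are applied before status is assigned, so that favourable patients certainly drop out. The SAP states no such order, and the closing sentence of 4.2 presupposes that some classification has already been made. A reader might also infer that only ITT is tied to 12 months; section 6 contradicts that. PP's own exclusions in 4.3 are not at fault, since PP has the problem only through 4.2 and 4.4.

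What does not fall away is the text of 4.2. It decides who is in the population, it does not refer to 6, 6.1.1 or the 3.1 sentence, and item 4 uses a term that 3.1 extends to the end of follow-up. Item 6 names 12 months; items 1, 4 and 5 do not. The SAP states no data cut for the 12-month analysis.

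It is also fair to say that equal removal with a positive difference makes non-inferiority harder to show, and that section 7 asks for consistent ITT results. But step 7 of the working shows that unequal removal can act in the other direction, and section 7 does not require ITT to meet the strict criterion.

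**Conclusion.** The point holds as an unresolved conflict in the rules that define both primary populations. Applied literally, those rules give a wrong 12-month analysis; read with sections 2, 3.1, 6 and 6.1.1, they probably were not meant to. The documents do not support saying that patients will be lost, or that the trial's conclusion will change.

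The size is conditional. The SAP gives no rate of loss, death or reinfection for months 12-24. Crossing 12 points with equal removal needs a result already close to the margin and, at 48 against 38 of 235, removal of about 10% of favourable patients per arm. Well inside the margin the effect is about half a point on the upper limit (6.7 to 7.2). Unequal removal matters more, because it creates a difference of 0.8 to 1.6 points from nothing in the cases shown. The stated sample size is unaffected.

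The text should be settled before database lock, since the choice of reading could otherwise be made with the results known.

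**What to change.** - **4.2 items 1, 4 and 5, and the loss rule in 4.4:** for the primary analysis, limit them to events before the 12-month status is established (week 50-54 window).
- **4.2 closing sentence:** extend it to patients already classified as favourable at 12 months.
- **6.1.3 and 6.1.4:** state that events first arising after the 12-month assessment do not count towards the primary endpoint, while later cultures may still be used to resolve a positive, contaminated or missing 12-month result. A hard cut on cultures at 12 months should be avoided. It would conflict with 3.3, which lets later negatives clear an isolated positive, and with 4.2 item 6, which allows patients to be brought back.
- **10.1:** state that populations and status are re-derived with a 24-month cut-off.

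The cost is a few sentences in the SAP and a date condition in the derivation programs. No further data or patients are needed.
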